11. ADVERSE EVENTS AND SERIOUS ADVERSE EVENTS

11.1 Definition of Adverse Events (AEs)

An adverse event can be defined as any untoward medical occurrence associated with the use of an intervention in humans after providing written informed consent for participation in the study until the end of study visit, whether considered intervention-related or not.

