4. SCHEDULE OF ASSESSMENTS

	Screening / Baseline (beginning of 1 st period)	3-month Visit (end of 1 st period, beginning of 2 nd period)	6-month Visit	9-month Visit (end of 2 nd period)
Informed consent	X			
Inclusion/exclusion criteria	X			
Complete ophthalmological examination*	X	X	X	X
Randomization to study sequence	X			
VFQ-25	X	X	X	X
SF-36	X	X	X	X
Dispensing treatment	X	X	X	
Concomitant medications	X	X	X	X
Adverse events		X	X	X

*Including visual acuity (VA), VF (24-2, SITA standard strategy), fundus assessment, biomicroscopy (with specific lens evaluation using Lens Opacities Classification System III (LOCS III) criteria), IOP assessment. Gonioscopy and optic nerve head (ONH) topography parameters measured by optical coherence tomography (OCT) are required at screening to verify inclusion/exclusion criteria.

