10. DESIGN

The trial will be a randomized, double-masked, placebo-controlled, cross-over study. Eligibility criteria will be assessed, and study procedures clearly explained when the potentially eligible patients are initially visited. If the patients accept to participate in the trial, they will have to sign the informed consent form. After this, the patients will be randomized in a 1:1 ratio to one of the two sequences of the cross-over design: Neurotidine[®]-placebo or placebo-Neurotidine[®]. The randomization will be stratified by centre.

- Baseline visit (beginning of 1st period): Enrolled patients will undergo a complete ophthalmologic examination with VA, VF (24-2, SITA standard strategy), fundus assessment, biomicroscopy (with specific lens evaluation using Lens Opacities Classification System III (LOCS III) criteria), IOP assessment. A masked to treatment evaluator will administer the two study questionnaires (VFQ-25 and SF-36). The patients will be given the bottles for the first 3-month period.
- 3-month visit (end of the 1st period and beginning of 2st period): Patients will undergo a complete ophthalmologic examination with VA, VF (24-2, SITA standard strategy),

biomicroscopy, IOP assessment. Patients will be asked about treatment side effects and all complains/considerations will be recorded. The two study questionnaires (VFQ-25 and SF-36) will be administered. The patients will be given the bottles for the second 3-month period.

- 6-month visit: Patients will undergo a complete ophthalmologic examination with VA, VF (24-2, SITA standard strategy), biomicroscopy, IOP assessment. Patients will be asked about treatment side effects and all complains/considerations will be recorded. Patients will be again administered the 2 study questionnaires (SF-36 and VFQ-25). The patients will be given the bottles for the third 3-month phase.
- 9-month visit (end of the 2st period): Patients will undergo a complete ophthalmologic examination with VA, VF (24-2, SITA standard strategy), biomicroscopy, IOP assessment. Patients will be asked about treatment side effects and all complains/considerations will be recorded. Patients will be administered the two study questionnaires (VFQ-25 and SF-36).

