11.2 Definition of Serious Adverse Events (SAEs)

An adverse event (AE) is considered "serious", regardless of relationship with the intervention, if, in the view of either the investigator or Sponsor, it results in any of the

following outcomes: death, a life-threatening adverse event, inpatient hospitalization or prolongation of existing hospitalization, a persistent or significant incapacity or substantial disruption of the ability to conduct normal life functions, or a congenital anomaly/birth defect. Important medical events that may not result in death, be life-threatening, or require hospitalization may be considered serious when, based upon appropriate medical judgment, they may jeopardize the participant and may require medical or surgical intervention to prevent one of the outcomes listed in this definition.

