11.4 Time Period and Frequency for Event Assessment and Follow-Up

The occurrence of an AE or SAE may come to the attention of study personnel during study visits and interviews of a study participant presenting for medical care, or upon review by a study monitor.

All AEs including local and systemic reactions will be captured on the eCRF. Information to be collected includes event description, time of onset, clinician's assessment of severity, relationship to intervention (assessed only by those with the training and authority to make a diagnosis), and time of resolution/stabilization of the event. All AEs occurring while on study must be documented appropriately regardless of relationship. All AEs will be followed to adequate resolution.

Any medical condition that is present at the time that the participant is screened will be considered as baseline and not reported as an AE. However, if the study participant's condition deteriorates at any time during the study, it will be recorded as an AE.

Changes in the severity of an AE will be documented to allow an assessment of the duration of the event at each level of severity. AEs characterized as intermittent require documentation of onset and duration of each episode.

The investigator will record all reportable events with onset dates occurring any time after informed consent is obtained until 30 days after the last treatment, and later if a causal

relationship with the intervention is suspected. At each study visit, the investigator will inquire about the occurrence of AE/SAEs since the previous visit. Events will be followed for outcome information until resolution or stabilization.

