11.6 Serious Adverse Event Reporting

Every SAE, regardless of suspected causality, occurring after the subject has provided informed consent and until at least 30 days after the subject has stopped study treatment must be reported to the Sponsor within 24 hours of site awareness.

Any SAE experienced after this 30-day period should only be reported to the Sponsor if the investigator suspects a causal relationship to the study treatment. Recurrent episodes, complications, or progression of the initial SAE must be reported as follow-up to the original episode within 24 hours of the investigator receiving the follow-up information.

Information about all SAEs will be transmitted to the Contract Research Organization (CRO) OPIS, in charge for this trial of vigilance for Food for Special Medical Purposes Neurotidine[®], via email at [contact] or by fax using the following number: [contact]. Any AE collected by OPIS will be promptly forwarded to Omikron Italia, which is Responsible for the Food for Special Medical Purposes Neurotidine[®].

All SAEs will be followed until satisfactory resolution or until the site investigator deems the event to be chronic or the adherence to be stable. Other supporting documentation of the event may be requested by the study Sponsor and should be provided as soon as possible.

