13. SAMPLE SIZE

The sample size has been calculated based on the main outcome of the study, i.e. the mean change vs baseline of the global score of The National Eye Institute 25-Item Visual Function Questionnaire (VFQ-25) in patients with moderate-stage glaucoma (*Ophthalmol 2015 Nov Acta 19*).

When the sample size in each sequence group is 100, (a total sample size of 200) a 2 x 2 crossover design will have 80% power to detect a difference in means of 3.0 (the difference between study treatment mean, μ_1 , of 3.0 and placebo mean, μ_2 , of 0) assuming that the crossover ANOVA \sqrt{MSE} is 10.607 (the standard deviation of differences, σ_d , is 15.0) using a two group t-test (crossover ANOVA) with a 0.05 two-sided significance level.

The total sample size is adjusted to 220 patients considering an expected dropout rate of about 10%.

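### Do the different end dates for adverse events in sections 11.1, 11.4 and 11.6 leave the safety summary without a usable event set?

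*Combined protocol and SAP*

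**What the plan says.** Section 11.1 defines an adverse event as one that arises "after providing written informed consent for participation in the study until the end of study visit, whether considered intervention-related or not". Section 11.4, which deals with timing, has the investigator record reportable "events with onset dates occurring any time after informed consent is obtained until 30 days after the last treatment", and later still when a causal link is suspected. Section 11.6 says that every SAE from consent "until at least 30 days after the subject has stopped study treatment must be reported to the Sponsor", within 24 hours of the site learning of it. Section 11.2 makes an SAE an adverse event that meets a seriousness criterion.

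On how events are found, section 11.4 says: "At each study visit, the investigator will inquire about the occurrence of AE/SAEs since the previous visit". The same section also accepts events that surface when a participant seeks medical care or when a monitor reviews records. It separately asks that everything occurring on study be documented. Sections 4 and 10 list no visit after month 9, the end of the second period.

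Section 14 describes adverse events by System Organ Class and Preferred Term, split by treatment group, and names no onset window. Section 7 lists safety and tolerability among the secondary outcomes.

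**The concern.** Read literally, the sections give two event sets. A hospitalisation on day 10 after the month-9 visit must be reported under 11.6. Yet 11.1 does not count it as an adverse event, although 11.2 makes every SAE one. A non-serious event on day 20 is in under 11.4 and out under 11.1. Section 14 does not say which rule feeds its summary, and it is the only planned analysis of a stated outcome. Two analysts could therefore report different counts.

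In a crossover, splitting by treatment group is also ambiguous: it can mean the randomised sequence or the product taken at onset. If it means product, events after the last dose need a convention that section 14 does not supply. No visit falls in those 30 days, so their ascertainment looks uneven as well.

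**Working it through.** **1. The plan's own figure.** Section 13 gives 100 patients per sequence, a difference of 3.0, a standard deviation of differences of 15.0 and a two-sided 0.05 level.

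- √MSE = 15/√2 = 10.607, as stated.
- Standard error = (15/2) × √(1/100 + 1/100) = 1.061, and 3/1.061 = 2.83.
- The noncentral t distribution gives 80.4% power, against the 80% stated.

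No adverse-event quantity enters this calculation, so the concern cannot affect it.

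**2. What each rule does in practice.**

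- *SAE on day 10 after month 9.* Outside the definition in 11.1, but 11.6 explicitly requires it to be reported. It is not lost.
- *Non-serious event on day 20 after month 9.* Outside 11.1, inside 11.4 if the undefined word reportable covers non-serious events. With no visit due, it is recorded only if it surfaces through medical care or monitoring. This is the core of the conflict.
- *Patient who stops treatment early but keeps attending.* Here the 11.1 window can be the longer one. The separate instruction in 11.4 to document everything on study keeps such events in.
- *Patient who leaves early without a final visit.* Section 11.1 gives no clear end date, but 11.4 does: 30 days after the last treatment. Section 13 implies about 220 − 200 = 20 dropouts in all.

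A site following 11.4 to 11.6 therefore has a workable rule in each case.

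**3. Size of the disputed window.** Take 200 completers, the last dose at the month-9 visit and a month of 365.25/12 = 30.44 days.

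- Extra time: 200 × 30 = 6,000 patient-days; 6,000/30.44 = 197 patient-months.
- Time on treatment: 200 × 9 = 1,800 patient-months.
- Ratio: 197/1,800 = 11.0%.

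The documents give no event rates, so a range is assumed. The same rate is applied on and off treatment:

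| Assumed rate per month | On treatment (1,800 patient-months) | Disputed window (197 patient-months) |
|---|---|---|
| 0.5% | 9 | 1.0 |
| 1% | 18 | 2.0 |
| 2% | 36 | 3.9 |

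The last column assumes full ascertainment. With no visit in the window, fewer would probably be recorded.

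**4. Balance between products.** With 1:1 allocation, 100 completers end on each product, so the window adds 100 × 30 = 3,000 patient-days, or about 99 patient-months, after each. Treatment time per product is 100 × 3 + 100 × 6 = 900 patient-months. If off-treatment rates do not depend on the last product taken, the same expected number *x* is added to both sides. The difference in counts is then unchanged: (a + x) − (b + x) = a − b. A ratio would move slightly towards 1, and listing post-treatment events separately avoids even that.

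**The case for a change.** The strongest case for a change is that the conflict is in the current text and cannot be argued away. Section 11.1 itself contains the end date, so it cannot be dismissed as a bare definition with the timing left to 11.4. Reading 11.4 as covering SAEs only does not help, because an SAE is a kind of adverse event. Section 14 uses the term that 11.1 defines, supplies no window and no rule for assigning events to a product, and is the only analysis of a stated outcome. Onset time is already collected, so aligning the wording would be cheap, and settling it before unmasking would prevent a choice of event set after the data are seen.

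The textual point stands in full. The consequence does not follow from it. That events after the last dose have nowhere to go depends on reading treatment group as product at onset. Section 14 applies the same phrase to medical history, which in a crossover can only be shown by sequence, and under a sequence reading every event has a place. Under a product reading, listing events after the last dose apart from those on treatment is ordinary practice. The worry about selective choice is weak when the disputed events are few, off treatment and evenly spread between products, and no test rests on them.

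**Conclusion.** The wording of 11.1 does not match 11.4 and 11.6, but no change to the plan is needed. The timing and reporting sections give sites a usable rule, SAEs through 30 days are explicitly covered, and onset times let analysts separate on-treatment from post-treatment events whichever end date is used. What section 14 leaves open is a reporting convention that analysts fill sensibly.

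The amount at issue is 30 days per completer, 11% on top of treatment time, or about 1 to 4 events at the assumed rates, with about 99 patient-months after each product. No directional bias is shown, and no conclusion about efficacy or the descriptive safety profile would turn on it.

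This rests on four assumptions: that the end-of-study visit in 11.1 is the month-9 visit, since none later is listed; that nearly all of the 200 patients complete; that event rates lie in the assumed range; and that off-treatment rates do not differ materially by last product. A much higher event rate would raise the counts in proportion on and off treatment, and the 11% would stay the same.

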11.2 Definition of Serious Adverse Events (SAEs)

An adverse event (AE) is considered "serious", regardless of relationship with the intervention, if, in the view of either the investigator or Sponsor, it results in any of the

following outcomes: death, a life-threatening adverse event, inpatient hospitalization or prolongation of existing hospitalization, a persistent or significant incapacity or substantial disruption of the ability to conduct normal life functions, or a congenital anomaly/birth defect. Important medical events that may not result in death, be life-threatening, or require hospitalization may be considered serious when, based upon appropriate medical judgment, they may jeopardize the participant and may require medical or surgical intervention to prevent one of the outcomes listed in this definition.

11.3 Classification of an Adverse Event

11.3.1 Severity of Event

The following guidelines will be used to describe severity:

- Mild – Events require minimal or no treatment and do not interfere with the participant’s daily activities.
- Moderate – Events result in a low level of inconvenience or concern with the therapeutic measures. Moderate events may cause some interference with functioning.
- Severe – Events interrupt a participant’s usual daily activity and may require systemic drug therapy or other treatment. Severe events are usually potentially life threatening or incapacitating. Of note, the term “severe” does not necessarily equate to “serious”.

11.3.2 Relationship to study intervention

All AEs must have their relationship to study intervention assessed by the clinician who examines and evaluates the participant based on temporal relationship and his/her clinical judgment. Investigators are to judge the causal relationship of the event with the study intervention as “suspected”, “unsuspected” or “unknown”.

11.3.3 Expectedness

The Sponsor will be responsible for determining whether an AE is expected or unexpected. An AE will be considered unexpected if the nature, severity, or frequency of the event is not consistent with the risk information previously described for the study intervention.

11.4 Time Period and Frequency for Event Assessment and Follow-Up

The occurrence of an AE or SAE may come to the attention of study personnel during study visits and interviews of a study participant presenting for medical care, or upon review by a study monitor.

All AEs including local and systemic reactions will be captured on the eCRF. Information to be collected includes event description, time of onset, clinician's assessment of severity, relationship to intervention (assessed only by those with the training and authority to make a diagnosis), and time of resolution/stabilization of the event. All AEs occurring while on study must be documented appropriately regardless of relationship. All AEs will be followed to adequate resolution.

Any medical condition that is present at the time that the participant is screened will be considered as baseline and not reported as an AE. However, if the study participant's condition deteriorates at any time during the study, it will be recorded as an AE.

Changes in the severity of an AE will be documented to allow an assessment of the duration of the event at each level of severity. AEs characterized as intermittent require documentation of onset and duration of each episode.

The investigator will record all reportable events with onset dates occurring any time after informed consent is obtained until 30 days after the last treatment, and later if a causal

relationship with the intervention is suspected. At each study visit, the investigator will inquire about the occurrence of AE/SAEs since the previous visit. Events will be followed for outcome information until resolution or stabilization.

11.5 Adverse Event Reporting

All identified AEs (serious and non-serious, related and unrelated) must be recorded and described on the eCRF.

11.6 Serious Adverse Event Reporting

Every SAE, regardless of suspected causality, occurring after the subject has provided informed consent and until at least 30 days after the subject has stopped study treatment must be reported to the Sponsor within 24 hours of site awareness.

Any SAE experienced after this 30-day period should only be reported to the Sponsor if the investigator suspects a causal relationship to the study treatment. Recurrent episodes, complications, or progression of the initial SAE must be reported as follow-up to the original episode within 24 hours of the investigator receiving the follow-up information.

Information about all SAEs will be transmitted to the Contract Research Organization (CRO) OPIS, in charge for this trial of vigilance for Food for Special Medical Purposes Neurotidine[®], via email at [contact] or by fax using the following number: [contact]. Any AE collected by OPIS will be promptly forwarded to Omikron Italia, which is Responsible for the Food for Special Medical Purposes Neurotidine[®].

All SAEs will be followed until satisfactory resolution or until the site investigator deems the event to be chronic or the adherence to be stable. Other supporting documentation of the event may be requested by the study Sponsor and should be provided as soon as possible.

11.7 Reporting Events to Participants

Should an event occur that changes the overall benefit/risk ratio of the study, the Sponsor shall evaluate if a risk minimization measure is needed. Should this measure require a substantial amendment to the protocol, the informed consent and patient information will be revised and submitted to the patient for written consent.

12. DATA MANAGEMENT**12.1 Data Handling and Record Keeping***12.1.1 Data Collection*

Designated investigator staff will enter the data required by the protocol into the eCRF using fully validated software that conforms to 21 CFR Part 11 requirements. Designated investigator site staff will not be given access to the Electronic Data Capture system until they are trained.

Web-based software will be used, and no installation procedure is needed. Each site will be authorized by the administrator to access the eCRF. Each site-qualified personnel will be allowed to access the eCRF by means of a 'login mask' requiring user ID and password and may read, modify, and update only the information entered at his or her site and according to their profile. Each page reports site code and subject code.

On-line validation programs will check for data discrepancies and, by generating appropriate error messages, allow the data to be confirmed or corrected before transfer to the CRO working on behalf of the Sponsor. The investigator will certify that the data entered in the eCRF are complete and accurate.

After database lock, the investigator will receive a CD-ROM of subject data for archiving at the investigational site.

12.1.2 Database management and quality control

The CRO working on behalf of the Sponsor will review the data entered in the eCRF by investigational staff for completeness and accuracy and instruct site personnel to make any necessary corrections or additions. The Data Manager will perform the cleaning session by reviewing the warning messages raised by on-line checks and by running post-entry checks by means of validation programs and data listings specific for the study. The occurrence of any protocol deviations will also be checked.

If clarifications are needed, the Data Manager will raise queries through the web application. Designated investigator site staff will be required to respond to queries and the Data Manager will make the correction to the database according to the responses.

Data collection and query flows, as well as the on-line and off-line checks, are detailed in the Data Management Plan and Data Validation documents.

Concomitant medications and prior medications entered into the database will be coded using the WHO Drug Reference List, which employs the ATC classification system. Medical history/current medical conditions and AEs will be coded using MedDRA.

The database will be locked after all the above actions have been completed and the database has been declared complete and accurate.

